## 5.3 Subgroup Analyses

We will not perform subgroup analyses for secondary outcomes.

## **6. SAFETY OUTCOMES**

AEs and SAEs, including participant deaths and hospitalizations, were monitored by study site physicians and reported to the DSMB in accordance with the DSMB protocol. Safety analyses will be conducted in the safety analysis set, defined as all participants who received at least one dose of the study treatment. Safety data, including laboratory parameters, will be summarized descriptively by treatment group, reporting the number and percentage of participants experiencing each AE or SAE.

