## 2.4. Intervention

Provide a brief description of the details of each intervention being assessed including any potential control arm. If applicable, describe study drugs with dosages. Also include details of incomplete administration of study intervention e.g. acceptable reduction in study treatment for toxicity (where applicable).

Eligible pregnant mothers were randomly assigned to two groups (n=157 each):

(1) **Intervention group** consuming daily supplements of one capsule containing multistrain probiotics [Chr. Hansen A/S, Hørsholm, Denmark; *Lactobacillus rhamnosus* GG (LGG), *Bifidobacterium animalis subsp. lactis* (BB-12), *L. acidophilus* (LA-5)] and two capsules of higher-dose omega-3 FAs [Blackmores Pty Ltd, Australia; 720 mg eicosapentaenoic acid (EPA), 480 mg docosahexaenoic acid (DHA) in total], or

(2) **Control group** consuming one placebo capsule of probiotics (Chr. Hansen A/S, Hørsholm, Denmark) and two capsules of standard-dose omega-3 FAs (Blackmores Pty Ltd, Australia; 360 mg EPA, 240 mg DHA in total).

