Both groups consumed the supplements from the 2nd trimester of pregnancy until 6-months postpartum, regardless of their breastfeeding status. Omega-3 FAs supplementation began at 22 weeks of pregnancy, while probiotics/placebo supplementation started at 26 weeks. The gestational age for all subjects was assessed using ultrasonography at the nearest community health center or [name] General Hospital by trained general practitioners. These start times were chosen due to the late recognition of pregnancy in our population and therefore to ensure uniform initiation for all participants. Additionally, probiotics/placebo supplementation commenced during the third trimester because of limited evidence regarding probiotics use in pregnancy before this period. The placebo probiotics capsules were indistinguishable from the active capsules in appearance, taste, and odor. Likewise, the omega-3 capsules appeared identical across groups. All mothers in both groups also received psychosocial stimulation and healthy eating modules. These modules were delivered once during pregnancy (at 30–34 weeks of gestation) and twice during postpartum (between 0–1 month and between 1–2 months after birth). In the study sample, the majority of infants were breastfed, thus likely receiving DHA via their mother's breastmilk in addition to their prenatal exposure. Outcomes assessments were performed at 36–38 weeks of gestational age for fetal brain volume and when children reached the age of 4–6 months for Bayley-III, BERA, and eye-tracking assessments. All participants, outcome assessors, and field and research teams were blinded to the allocation of the intervention.

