## 2.7. Study Procedures

Mothers in intervention and control groups consumed the supplements from the 2nd trimester of pregnancy until 6 months post-partum, regardless of their breastfeeding status. Outcomes assessments were performed at 36–38 weeks of gestational age for fetal brain volume and when children reaching the age of 4–6 months for Bayley-III, BERA, and eye-tracking assessments. Fetal brain growth was assessed using MRI, and infant development was evaluated using the Bayley-III for cognitive scores and other developmental scores, BERA for auditory function, and eye-tracking assessments, which included the IOWA and VPC tasks for attention and memory indicators.

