#### **3.6. Definitions related to Adverse Events (AEs)**

- *Adverse Event* means any undesirable clinical experience, including clinically significant laboratory values, occurring to the subject during the study, whether or not considered related to the investigational product or the study procedures. This includes exacerbations of pre-existing conditions.
- *Adverse Effect*: When an Adverse Event has been determined to be related to the test product or the study procedures, it is considered an Adverse Effect.
- *Exacerbations of Pre-existing Conditions* means a condition that developed before the study but which worsened or occurred with increasing frequency as study progressed.
- *“Unexpected” Adverse Events* are defined as those that would not be expected among subjects who are supplemented with the test product at safe levels.
- *Serious Adverse Event (SAE)* means any event that results in death, is immediately life threatening requires inpatient hospitalization, results in persistent or significant disability/incapacity, or is a congenital anomaly/birth defect.
- *Life-Threatening* means the subject is at immediate risk of death from the event as it occurred.

The intensity of the Adverse Event was rated as mild, moderate, or severe using the following criteria:

- Mild events require minimal or no treatment and do not interfere with the subject's daily activities.
- Moderate events result in a low level of inconvenience or concern for the therapeutic measures. Moderate events may cause some interference with functioning.
- Severe events interrupt a subject's usual daily activity and typically require systemic drug therapy or other treatment. Severe events are usually incapacitating.

If any, changes in the intensity of an AE were documented to allow an assessment of the duration of the event to be performed at each level of intensity.

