## 4. DESCRIPTIVE STATISTICS

### 4.1. Recruitment and Follow-up

The status of participants will be reported using a CONSORT flowchart. Caregivers were informed that the children could withdraw from the study at any time. A senior staff person visited caregivers who indicated that the children wanted to withdraw to discuss the family's concerns and reasons for withdrawal. Children who had already withdrawn their participation were not followed up on unless they requested to rejoin the trial. All procedures related to recruitment, follow-up, and withdrawal were conducted in accordance with the trial's ethical approvals.

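### One safety set defined by dosing and one percentage of participants leave offspring risk not cleanly estimable, because only the mothers were dosed

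*SAP*

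**What the plan says.** Section 6 defines one safety set: "Safety analyses will be conducted in the safety analysis set, defined as all participants who received at least one dose of the study treatment". The summary is descriptive, by treatment group, "reporting the number and percentage of participants experiencing each AE or SAE".

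Other sections say who was dosed and who was exposed:

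- Section 2.4: "Eligible pregnant mothers were randomly assigned to two groups (n=157 each"). Section 2.7 confirms that mothers took the supplements, from the second trimester to six months after birth. No section describes a capsule given to a child.
- Section 2.4 on the infants: most were breastfed, "thus likely receiving DHA via their mother's breastmilk in addition to their prenatal exposure".
- Section 3.6: a serious adverse event includes one that "results in persistent or significant disability/incapacity, or is a congenital anomaly/birth defect". The person affected is called the subject, a term not defined as mother, child or pair.
- Section 4.1 on withdrawal: "Caregivers were informed that the children could withdraw from the study at any time". Sections 2.7.2 and 2.7.3 also call the assessed children study participants.

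No section defines a fetal or infant safety set, places a child in the safety set through the mother's dosing, or names a denominator for fetal, neonatal or infant events.

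**The concern.** The dosing condition suits a trial in which the person who takes the product is the person at risk. Here two people are exposed and only one is dosed. The SAP foresees events in the other: in women enrolled in the second trimester, a congenital anomaly is chiefly an event of the child. Section 6 does not say in whose row such an event is entered or what it is divided by.

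What is at stake is what the trial can report about harm in fetuses and infants, on whom all its efficacy hypotheses are measured. If infant events are dropped, the safety table is silent about them. If they are entered under the mother, the infant percentage has the wrong denominator, and summary rows no longer describe either mothers or infants. The choice is also left open until the data are in hand.

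**Working it through.** The SAP states no figure on this point, so there is none to reproduce. The check compares the possible readings of section 6 and then illustrates the size.

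**Step 1. Two readings of participants who received a dose.**

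| Reading | Are infants in the set? | Denominator for an infant event | Pooled rows |
|---|---|---|---|
| Literal: the person who took a capsule | No | None | Mothers only |
| Pair: mother and child, if the mother took a capsule | Yes, through the mother | Dosed mothers | Mother and infant counted as one participant |

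Neither reading gives infant events over live births, or events before birth over pregnancies or fetuses.

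**Step 2. What the pair reading does to a pooled row.** Let m mothers and c infants in an arm be hospitalised, with b pairs in which both were. Counted by participant, the row is (m + c − b)/157. With assumed values m = 3, c = 5, b = 1, it reads 7/157 = 4.5%. The maternal risk would be 3/157 = 1.9%, and the infant count over mothers 5/157 = 3.2%. The row shows neither, and they cannot be recovered from it.

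**Step 3. What the denominator does to an infant percentage.** Inputs: 157 women per arm (section 2.4). The 5 infant events and the loss fractions are assumptions, except that 33.3% is the attrition anticipated in section 2.6, borrowed here as an outer case.

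- Over dosed mothers: 5/157 = 3.2%
- 5% of infants lost: 157 × 0.95 ≈ 149; 5/149 = 3.4%
- 20% lost: 157 × 0.80 ≈ 126; 5/126 = 4.0%
- 33.3% lost: 157 × 0.667 ≈ 105; 5/105 = 4.8%

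If losses differ by arm, the comparison between arms shifts as well.

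**Step 4. What could be said if no event occurred.** The exact two-sided 95% upper bound for 0/n is 1 − 0.025^(1/n).

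- n = 157: 1 − 0.025^(1/157) = 2.3%
- n = 105: 1 − 0.025^(1/105) = 3.5%

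The first assumes one live-born, fully observed infant per randomised woman. The SAP does not give the number of live births.

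**The case against.** The strongest reply is that the SAP already places children in an analysis set through their mothers. No child was randomised either, yet section 3.9 defines the efficacy set as all randomised subjects, and Table 2 applies the randomised treatment to infant Bayley-III and BERA outcomes. Read the same way, the safety set is dosed mother-infant pairs. The table would then show offspring events by arm. Section 3.6.1 codes events by ICD-10, so a birth defect and a maternal diagnosis would normally sit on different lines.

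This reply stands in part. A reader might infer from the dosing rule that offspring have no safety denominator at all, or that the table could support no statement about them. The documents do not support that: the pair reading is available, and mixing is then mostly confined to pooled rows. But the SAP never states that reading, and under it infant events are still divided by dosed mothers.

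A second reply is that section 2 states the safety aim for supplementation of healthy pregnant women, that section 6 refers monitoring and reporting to the DSMB protocol, and that the trial protocol may say whether infants were subjects for adverse events. It is true that the collection of infant events may be settled there. The safety set and the summary measure, however, are fixed in section 6 itself.

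A third reply is that the supporting text is thin. Congenital anomaly is one limb of a general definition, and section 4.1 concerns withdrawal, not adverse event status. This also stands in part: neither shows that infants had their own adverse event records. They do show that the SAP anticipates offspring events and treats children as people in the study.

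**Conclusion.** The point holds as a badly fixed rule. Section 6 uses one dosing-based set and one percentage of participants for a trial with two exposed populations. Depending on the reading, infant events are either left out or divided by dosed mothers, with maternal and infant events mixed in pooled rows. Offspring risk is therefore not cleanly estimable from the planned table.

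The size cannot be taken from the document. The 2.3% and 3.5% bounds and the 3.2% to 4.8% range are illustrations that rest on assumed counts, one observed live birth per woman, or a loss figure taken from the sample-size section and not from safety follow-up.

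Safety is summarised descriptively, so no test and no efficacy conclusion depends on this. Nor does the SAP show that offspring events went unrecorded: the defect is in the analysis set and the denominator, not demonstrably in data collection.

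**What to change.** In section 6, replace the single set with two:

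1. **Maternal safety set:** women who took at least one dose.
2. **Offspring safety set:** all fetuses and live-born infants of those women, analysed in the mother's arm whether or not the child was later assessed.

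Tabulate maternal and offspring adverse events and serious adverse events separately. Use pregnancies (or fetuses) as the denominator for events before birth, and live births for infant events such as congenital anomaly, hospitalisation and death. Do this as far as the adverse event forms identify who had the event, and state any limit on the ascertainment of infant events.

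The cost is a few sentences, one more descriptive table, and the work of assigning recorded events to mother or infant. No section says that infant events were recorded separately from the mother's. If they were not, new wording cannot supply the infant table in full, and the report should say so.

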## 7. TABLES AND FIGURES

### 7.1. List of Tables

Table 1	Characteristics of the study sample
Table 2	Primary estimands
Table 3	Secondary estimands

